6.2.2.10 Management of hepatitis reactivation / flare

Reactivation of Hepatitis B (HBV) has been observed in patients with cancer receiving chemotherapy (Yeo 2004). Sporadic cases of Hepatitis B reactivation have also been seen in this setting with everolimus. Use of antivirals during anti-cancer therapy has been shown to reduce the risk of Hepatitis B virus reactivation and associated morbidity and mortality (Loomba 2008). A detailed assessment of Hepatitis B/C medical history and risk factors must be done for all patients at screening, with testing performed prior to the first dose of everolimus.

Monitoring and prophylactic treatment for hepatitis B reactivation

Table 6-4 provides detail of monitoring and prophylactic therapy according to the screening results of viral load and serologic markers testing.

Table 6-4 Action to be taken based on screening hepatitis B results

Test	Result	Result	Result	Result	Result
HBV-DNA	+	+ or -	-	-	-
HBsAg	+ or -	+	-	-	-
HBsAb	+ or -	+ or -	+ and no prior HBV vaccination	+ or -	- or + with prior HBV vaccination
HBcAb	+ or -	+ or -	+ or -	+	-
Recommendation	Prophylaxis treatment should be started 1-2 weeks prior to first dose of Everolimus Monitor HBV-DNA approximately every 4-8 weeks		No prophylaxis Monitor HBV-DNA approximately every 3-4 weeks		No specific action

Antiviral prophylaxis therapy should continue for at least 4 weeks after last dose of Everolimus. For HBV reactivation definition and management guidelines, see Table 6-5.

Table 6-5 Guidelines for the management of hepatitis B reactivation

HBV reactivation (with or without clinical signs and symptoms)*

For patients with baseline results: Positive HBV-DNA OR positive HBsAg reactivation is defined as: [Increase of 1 log in HBV-DNA relative to baseline HBV-DNA value OR new appearance of measurable HBV-DNA]	Treat: Start a second antiviral medication AND Discontinue Everolimus administration.
For patients with baseline results: Negative HBV-DNA and HBsAg AND [Positive HBsAb (with no prior history of vaccination against HBV), OR positive HBcAb] Reactivation is defined as: New appearance of measurable HBV-DNA	Treat : Start first antiviral medication AND Discontinue Everolimus

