* All reactivations of HBV are to be recorded as grade 3 (e.g. CTCAE Version 3.0 - Investigations/Other: Viral Reactivation), unless considered life threatening by the investigator, in which case they should be recorded as grade 4. Date of viral reactivation is the date on which the rise or reappearance of HBV-DNA was recorded.

Monitoring for hepatitis C flare

The following two categories of patients should be monitored every 4–8 weeks for HCV flare:

- Patients with detectable HCV RNA-PCR test at screening.
- Patients known to have a history of HCV infection, despite a negative viral load test at screening (including those that were treated and are considered ‘cured’)

For definitions of HCV flare and actions to be taken in the event of a flare, please refer to Table 6-6.

Table 6-6 Guidelines for the management of hepatitis C flare

Baseline results	HCV flare definition*	HCV flare management
Detectable HCV-RNA	> 2 log ₁₀ IU/mL increase in HCV-RNA AND ALT elevation > 5 x ULN or 3 x baseline level, whichever is higher.	Discontinue Everolimus
Knowledge of past hepatitis C infection with no detectable HCV-RNA	New appearance of detectable HCV-RNA AND ALT elevation > 5 x ULN or 3 x baseline level, whichever is higher.	Discontinue Everolimus

* All flares of HCV are to be recorded as grade 3 (e.g. CTCAE Version 3.0 - Investigations - Other: Viral Flare), unless considered life threatening by the investigator; in which case they should be recorded as grade 4. Date of viral flare is the date on which both the clinical criteria described above were met. (e.g., for a patient whose HCV-RNA increased by 2 logs on 01 JAN 2011 and whose ALT reached $> 5 \times$ ULN on 22 JAN 2011, the date of viral flare is 22 JAN 2011).

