7.1 Study flow and visit schedule

Table 7-1 Visit evaluation schedule

	Screening / Baseline	RT Day 22	RT Day 43	Post RT day 15	Post RT day 22	Post RT week 6	Post RT week 14	Post RT week 26
Visit no.	1	2	3	4	5	6	7	8
Treatment days*	-21 to -1							
Demography/informed consent (D)	X							
Inclusion/exclusion criteria (D)	X							
Relevant medical history/current medical conditions (D)	X							
Diagnosis and extent of cancer (D)	X							
Prior/post antineoplastic therapy (D)	X							
HIV history (S)	X							
Vital signs (D)	X	X	X	X	X	X	X	X
Height (D)	X							
Weight (D)	X	X	X	X	X	X	X	X
Physical examination (S)	X	X	X	X	X	X	X	X
ECOG performance status (D)	X	X			X	X	X	X
EKG ¹ (D)			X					
Correlative studies	X	X	X	X	X	X	X	X
Hematology ² (D)	X		X	X	X			
Coagulation (D)	X		X	X	X			
Biochemistry ³ (D)	X		X	X	X			
Serum Lipid Profile ⁴ (D)	X		X	X	X			
Prior/concomitant medications (D)	X			X	X			

	Screening / Baseline	RT Day 22	RT Day 43	Post RT day 15	Post RT day 22	Post RT week 6	Post RT week 14	Post RT week 26
Visit no.	1	2	3	4	5	6	7	8
Treatment days*	-21 to -1							
Everolimus ⁵				X				
HBV-DNA, HBsAg, HBs Ab, HBc Ab, HCV-RNA-PCR ⁶ (D)	X							
HBV DNA, HCV RNA-PCR ⁷ (D)	X							

* (+/- 1 day for visits 2,3,4,5; +/- 1 week for visits 6,7,8)

1. Baseline ECG is a standard 12 lead and must be performed within 21 days of first dose for patients enrolled and may be repeated at the investigator's discretion if clinically indicated
2. Hematology tests include a complete blood count (CBC). A total white blood cell (WBC) with absolute differentials (including neutrophil count plus bands, lymphocyte, monocyte, eosinophil, basophil counts), red blood cells (RBC), hemoglobin (Hgb), and a platelet count.
3. Serum Chemistry must include: BUN or uric acid, creatinine, LDH, total protein, electrolytes (sodium, potassium and calcium), total bilirubin, GGT, albumin, alkaline phosphatase, AST/sGOT fasting glucose.
4. Serum fasting lipid profile must include: total cholesterol and triglycerides. Patients should be in fasting state.
5. Everolimus is taken once daily for a total of five days, with drug dispensed at Visit 4.

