6. All patients should be screened for hepatitis risk factors and any past illnesses of hepatitis B and hepatitis C. It is highly recommended that patients positive HBV-DNA or HBsAg are treated prophylactically with an antiviral for 1-2 weeks prior to receiving study drug (see Section 6.7.3). The antiviral treatment should continue throughout the entire study period and for at least 4 weeks after the last dose of study drug. Patients with viral hepatitis C risk factors should be screened for HCV RNA-PCR.
7. Patients on antiviral prophylaxis treatment or positive HBV antibodies should be tested for HBV-DNA according to study visit schedule. Patients with positive HCV-RNA PCR or a history of past infection, even if treated and considered 'cured' – should be followed by HCV-RNA PCR according to visit

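### Table 7-1 schedules HBV-DNA and HCV-RNA testing only at screening, but its own footnote 7 and Section 6.2.2.10 call for follow-up testing in patients who remain eligible

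*Protocol*

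**What the plan says.** **Table 7-1 (Section 7.1).** Two rows deal with viral hepatitis. The first, carrying footnote 6, is the screening panel: HBV-DNA, the HBV serological markers and HCV-RNA PCR. The second, carrying footnote 7, is "HBV DNA, HCV RNA-PCR". Each has a single tick, in the Screening/Baseline column. Everolimus is ticked at visit 4 (post-RT day 15).

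**Footnote 7.** "Patients on antiviral prophylaxis treatment or positive HBV antibodies should be tested for HBV-DNA according to study visit schedule". Patients with a positive HCV-RNA result or a past infection, even one regarded as cured, "should be followed by HCV-RNA PCR according to visit".

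**Section 6.2.2.10.** For patients who are HBV-antibody positive (not explained by vaccination) but negative for HBV-DNA and HBsAg, Table 6-4 says: "Monitor HBV-DNA approximately every 3-4 weeks". HCV monitoring is every 4-8 weeks and includes "Patients known to have a history of HCV infection, despite a negative viral load test at screening". Under Table 6-5, reactivation in the antibody-only group means that HBV-DNA becomes measurable for the first time, whether or not the patient has symptoms. The note to that table says: "All reactivations of HBV are to be recorded as grade 3", or grade 4 if life-threatening.

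**Exclusion 5c (Section 5.1).** This removes patients with HBV-DNA or HCV-RNA that can be quantified, and those positive for HBsAg. It does not remove patients with HBV antibodies only, or past HCV without quantifiable RNA.

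**DLT (Sections 4.1, 6.1 and 9.1).** Any adverse event of grade 3 or above that is related to everolimus.

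**The concern.** Footnote 7 defers to a visit schedule that contains no follow-up test. The row it annotates repeats, at the same visit, assays already in the row above; it has a purpose only as a follow-up row.

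The visit table is what sites usually work from day to day. If it is followed without the text, an antibody-positive patient has no HBV-DNA result after everolimus. For that patient reactivation is defined by the assay alone, so a symptom-free event would go unseen. That matters for the patient: Section 8.1.1 notes that reactivation with everolimus has been fatal in some cases. It also touches the dose decision, because one DLT among the first three patients expands the 5 mg cohort to six and two DLTs prevent escalation.

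The only ticked test also precedes radiotherapy and any chemotherapy. Section 6.2.2.10 itself reports HBV reactivation in patients receiving chemotherapy. With no test near the start of everolimus, a positive result found later would be hard to attribute to the drug, and the DLT definition depends on that attribution.

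**Working it through.** The plan states no figure to reproduce. The check compares the texts and then the visit spacing.

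1. **Are the affected patients in the trial?** Exclusion 5c removes the HBV-DNA- or HBsAg-positive groups in Table 6-4 and those with quantifiable HCV-RNA. It leaves the antibody-only HBV group and past HCV with a negative screening test. Table 6-4 and the HCV text name both for monitoring, and Tables 6-5 and 6-6 define an event for both.

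2. **What does the table schedule?** In the footnote 7 row: visit 1, one tick; visits 2 to 8, none. Visits 5 to 8 follow dosing, so 0 of 4 post-everolimus visits carry the test.

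3. **When is the one ticked test?** Screening is day -21 to -1. Assume RT ends on RT day 43 (visit 3), so the first dose falls on day 43 + 15 = 58. With no day 0:
   - from day -1: 58 + 1 - 1 = 58 days, 58/7 = 8.3 weeks before the first dose;
   - from day -21: 58 + 21 - 1 = 78 days, 78/7 = 11.1 weeks before.
   - If RT ends between day 40 and day 50, the range is 55/7 = 7.9 to 85/7 = 12.1 weeks.

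4. **Would ticking the later visits be enough?** Take post-RT weeks 6, 14 and 26 as days 42, 98 and 182, with visit 4 on day 15 and visit 5 on day 22. The table allows +/- 1 day at visits 2 to 5 and +/- 1 week at visits 6 to 8.

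| Visit | Weeks from first dose | Gap from previous visit | Gap with windows |
|---|---|---|---|
| 5 | (22 - 15)/7 = 1.0 | - | - |
| 6 | (42 - 15)/7 = 3.9 | (42 - 22)/7 = 2.9 weeks | 12 to 28 days, 1.7 to 4.0 weeks |
| 7 | (98 - 15)/7 = 11.9 | (98 - 42)/7 = 8.0 weeks | 6 to 10 weeks |
| 8 | (182 - 15)/7 = 23.9 | (182 - 98)/7 = 12.0 weeks | 10 to 14 weeks |

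Against the HBV interval of about 3-4 weeks, the last two gaps are too long even at the favourable end of the windows. Against the HCV interval of 4-8 weeks, the nominal 8-week gap sits at the limit and the 12-week gap exceeds it. Neither Table 6-4 nor the HCV text says how long monitoring continues after a five-day course, so the number of post-dose tests intended cannot be derived.

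5. **Which event is clearly at risk of being missed?** HBV reactivation in antibody-only patients, because it rests on HBV-DNA alone. An HCV flare also needs an ALT rise (Table 6-6), so the argument there is less direct.

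**The case against.** The strongest reply is that the protocol does direct the testing. Section 6.2.2.10 gives intervals for exactly these patients, and footnote 7 speaks of following them over visits, which cannot mean one screening sample. A site reading either text would test. This stands: a reader might infer from the table that such patients are never tested after everolimus, and the protocol as a whole does not say that. What remains is that the operational table contradicts its own footnote and the text. The way to the text is also poorly signposted: Section 5.1 sends the reader to Section 6.2.3.10 and footnote 6 to Section 6.7.3, whereas the guidance is in 6.2.2.10.

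Other limits also stand:

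- The language is advisory (should, recommendation), so calling the tests mandatory would be too strong.
- A reader might infer that the 3-4 week and 4-8 week intervals conflict. They do not: they apply to different patient groups and viruses. The only tension is between each interval and the visit spacing.
- A reader might infer that the DLT count will be wrong. The documents give neither the prevalence of these patients nor a reactivation rate. They call HBV reactivation with everolimus sporadic, and a DLT must also be drug-related. A missed DLT is possible; its probability cannot be estimated.
- The two hepatitis rows sit in the continued part of a table read from PDF, and footnote 7 ends mid-phrase, so a lost tick cannot be wholly ruled out. The everolimus tick in the same part falls correctly at visit 4, so column positions seem to have survived.

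**Conclusion.** The contradiction holds. The row annotated by footnote 7 shows one test, at screening, and none at the four visits after everolimus. Footnote 7 and Section 6.2.2.10 call for repeated testing in two groups that exclusion 5c leaves eligible. On this point the table is wrong as written.

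Its weight is small. It concerns whichever of the 10 to 16 treated patients have HBV antibodies or past HCV, a number the documents do not let one estimate. It does not affect the salivary-flow endpoint. The harm arises only where a site works from the table and not from the text. It is still worth correcting, because the event at issue can be silent, is graded 3 or higher by rule, and can enter a dose decision that turns on one or two events.

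The conclusion rests on the ticks having been read correctly from the table. The timing of the screening test also assumes that RT ends about day 43; the contradiction itself does not depend on that date.

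**What to change.** Reconcile the footnote 7 row of Table 7-1, footnote 7 and Section 6.2.2.10, so that the schedule shows, for each patient group, the follow-up testing the text calls for. Adding ticks at existing visits would not settle it, because the 8- and 12-week gaps after visit 6 do not fit the stated intervals. The sponsor therefore also has to decide and state when the tests fall and how long monitoring continues after the five-day course. Which of the existing texts should prevail is a clinical decision for the sponsor. The cross-references to Sections 6.2.3.10 and 6.7.3 can be corrected in the same edit.

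The cost is a table and footnote edit, plus a few assays, in the few patients concerned, that the text already calls for. Sample size, endpoints and analysis are unchanged.

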7.2 Assessment types

7.2.1 Pregnancy and assessments of fertility

There are no adequate data from the use of everolimus in pregnant women. Studies in animals have shown reproductive toxicity effects including embryo-toxicity and feto-toxicity. The potential risk for humans is unknown. Everolimus should not be given to pregnant women unless the potential benefit outweighs the potential risk to the fetus. If a pregnancy occurs while on study treatment, the newborn will be followed for at least 12 months.

It is not known whether everolimus is excreted in breast milk. However, in animal studies everolimus and/or its metabolites readily passed into the milk of lactating rats. Women taking everolimus should therefore not breast-feed.

Women of childbearing potential

Women of child-bearing potential, defined as all women physiologically capable of becoming pregnant, (including female pediatric patients who are menarcheal or who become menarcheal during the treatment) must use highly effective contraception during the study and for 8 weeks after stopping treatment. Highly effective contraception is defined as either:

- Total abstinence: When this is in line with the preferred and usual lifestyle of the subject. [Periodic abstinence (e.g., calendar, ovulation, symptothermal, post-ovulation methods) and withdrawal are not acceptable methods of contraception]
- Female Sterilization: have had surgical bilateral oophorectomy (with or without hysterectomy), total hysterectomy or tubal ligation at least six weeks before taking study treatment. In case of oophorectomy alone, only when the reproductive status of the woman has been confirmed by follow up hormone level assessment
- Male partner sterilization: The vasectomized male partner should be the sole partner for that subject with the appropriate post-vasectomy documentation of the absence of sperm in the ejaculate.
- Use of oral, injected or implanted hormonal methods of contraception or placement of an intrauterine device (IUD) or intrauterine system (IUS) or other forms of hormonal contraception that have comparable efficacy (failure rate <1%), for example, hormone vaginal ring or transdermal hormone contraception. In case of use of oral contraception women should have been stable on the oral agent for a minimum of 3 months before taking everolimus.

Male Contraception

Sexually active males must use a condom during intercourse while taking the drug and for 8 weeks after stopping treatment and should not father a child in this period.

A condom is required to be used also by vasectomised men in order to prevent delivery of the drug via seminal fluid.

Female partners of male patients must also be advised to use one of the following contraception methods: Use of (1) oral, injected, implanted or other hormonal methods of contraception, or (2) intrauterine device (IUD) or intrauterine system (IUS), or (3) prior male/female sterilization.

Fertility

The potential for everolimus to cause infertility in male and female patients is unknown. However, menstrual irregularities, secondary amenorrhea and associated luteinizing hormone (LH)/follicle stimulating hormone (FSH) imbalance has been observed.

Based on non-clinical findings, male and female fertility may be compromised by treatment with everolimus.

7.2.2

CORRELATIVES:

The decrease of saliva flow rates (compared to baseline prior to definitive treatment) during radiotherapy treatment at 3, 6 weeks and prior to everolimus administration and the subsequent recovery of saliva flow rates at completion of the 5 day everolimus course and 1, 3 and 6 months after RT/chemoRT completion to determine the kinetics and stability of saliva flow rate recovery.

The production of the saliva protein amylase also decreases with salivary gland dysfunction following irradiation. Hence, we will measure protein composition within the saliva on an Experion microfluidic chip as previously described by the [name] lab (Grundmann 2010, Morgan-Bathke 2014, Hill 2014).). Briefly, a small amount of saliva (1-2 µl) will be loaded on the Experion microfluidic chips according to manufacturer's instructions. Sample analysis will focus on the profile and concentration of all proteins present in saliva. Percent decrease and recovery of amylase will be measured at all available time points and confirmed using immunoblotting techniques.

Surveys that will administered include:

- a. Xerostomia Inventory survey (Thomson 1999, appendix A)
- b. Xerostomia Visual Analog Scale survey (Pai 2001, appendix B)

8 Safety monitoring and reporting

Information about all adverse events, whether volunteered by the subject, discovered by investigator questioning, or detected through physical examination, laboratory test or other means, will be collected and recorded and followed as appropriate.

8.1 Adverse events

8.1.1 Definitions and reporting

An adverse event is defined as the appearance of (or worsening of any pre-existing) undesirable sign(s), symptom(s), or medical condition(s) that occur after patient's signed informed consent has been obtained.

Abnormal laboratory values or test results occurring after informed consent constitute adverse events only if they induce clinical signs or symptoms, are considered clinically significant, require therapy

(e.g., hematologic abnormality that requires transfusion or hematological stem cell support), or require changes in study medication(s).

Adverse events that begin or worsen after informed consent should be recorded *in the Adverse Events CRF*. Conditions that were already present at the time of informed consent should be recorded *in the Medical History page of the patient's CRF*. Adverse event monitoring should be continued for at least 30 days (or 5 half-lives, whichever is longer) following the last dose of study treatment. Adverse events (including lab abnormalities that constitute AEs) should be described using a diagnosis whenever possible, rather than individual underlying signs and symptoms. When a clear diagnosis cannot be identified, each sign or symptom should be reported as a separate Adverse Event. Adverse events will be assessed according to the Common Terminology Criteria for Adverse Events (CTCAE) version 4.0.

If CTCAE grading does not exist for an adverse event, the severity of mild, moderate, severe, and life-threatening, corresponding to Grades 1 - 4, will be used.

The occurrence of adverse events should be sought by non-directive questioning of the patient (subject) during the screening process after signing informed consent and at each visit during the study. Adverse events also may be detected when they are volunteered by the patient (subject) during the screening process or between visits, or through physical examination, laboratory test, or other assessments. As far as possible, each adverse event should be evaluated to determine:

1. The severity grade (CTCAE Grade 1-4)
2. *Its duration (Start and end dates) (add or Ongoing at End of Study for)*
3. *Its relationship to the study treatment (Reasonable possibility that AE is related: No, Yes or*
Its relationship to the study treatment (Reasonable possibility that AE is related: No, Yes, investigational treatment, Yes, the study treatment (non-investigational), Yes, both and/or indistinguishable)
4. *Action taken with respect to study or investigational treatment (none, dose adjusted, temporarily interrupted, permanently discontinued, unknown, not applicable)*
5. *Whether medication or therapy was given (no concomitant medication/non-drug therapy, concomitant medication/non-drug therapy)*
6. *Whether it is serious, where a serious adverse event (SAE) is defined as in Section 8.2.1 and which seriousness criteria have been met*

Outcome (not recovered/not resolved, recovered/resolved, recovering/resolving, recovered/resolved with sequelae, fatal, unknown) If the event worsens the event should be reported a second time in the CRF noting the start date when the event worsens in toxicity. For grade 3 and 4 adverse events only, if improvement to a lower grade is determined a new entry for this event should be reported in the CRF noting the start date when the event improved from having been Grade 3 or Grade 4.

Any AE that constitutes a DLT will be reported like a grade 3 and 4 adverse event.

All adverse events should be treated appropriately. If a concomitant medication or non-drug therapy is given, this action should be recorded on the Adverse Event CRF.

Once an adverse event is detected, it should be followed until its resolution or until it is judged to be permanent, and assessment should be made at each visit (or more frequently, if necessary) of any

Dignity Health
Research Institute

IRB NUMBER: PHXB-17-0072-70-15

IRB APPROVAL DATE: 07/03/2018

changes in severity, the suspected relationship to the study treatment, the interventions required to treat it, and the outcome.

Any and all adverse events will be recorded on the UACC adverse events record form and reviewed by the Principal Investigator.

NOTE : This only applies to non-interventional trials. All non-serious AEs suspected to be causally related to the Novartis drug of focus i.e. ADRs must be periodically transferred to Novartis.

Adverse Drug Reactions

Oncology

The most common ADRs, suspected to be related to treatment by the investigator (incidence $\geq 1/10$) from the pooled safety data were (in decreasing order): stomatitis, rash, fatigue, diarrhea, infections, nausea, decreased appetite, anemia, dysgeusia, pneumonitis, edema peripheral, hyperglycemia, asthenia, pruritus, weight decreased, pruritus, asthenia, peripheral edema, hypercholesterolemia, epistaxis, cough and headache.

The most common grade 3/4 ADRs, suspected to be related to treatment by the investigator (incidence $\geq 1/100$ to $<1/10$) were stomatitis, anemia, hyperglycemia, fatigue, infections, pneumonitis, diarrhea, asthenia, thrombocytopenia, neutropenia, dyspnea, lymphopenia, proteinuria, hemorrhage, hypophosphatemia, rash, hypertension, aspartate aminotransferase (AST) increased, alanine aminotransferase (ALT) increased, and pneumonia and diabetes mellitus.

The below table presents the frequency category of ADRs reported in the pooled safety analysis.

ADRs are listed according to MedDRA system organ class. Within each system organ class, the adverse reactions are ranked by frequency, with the most frequent reactions first. In addition, the corresponding frequency category using the following convention (CIOMS III) is also provided for each adverse reaction: very common ($\geq 1/10$); common ($\geq 1/100$ to $<1/10$); uncommon ($\geq 1/1,000$ to $<1/100$); rare ($\geq 1/10,000$ to $<1/1,000$); very rare ($<1/10,000$)

Infections and infestations

Very common - Infections^a

Blood and lymphatic system disorders

Very common	- Anemia,
Common	- Thrombocytopenia, neutropenia, leukopenia, lymphopenia
Uncommon	- Pancytopenia
Rare	- Pure red cell aplasia

Immune system disorders

Uncommon - Hypersensitivity

Metabolism and nutrition disorders

Very common - Decreased appetite, hyperglycemia, hypercholesterolemia
Common - Hypertriglyceridemia, hypophosphatemia, diabetes mellitus, hyperlipidemia, hypokalemia, dehydration

Psychiatric disorders

Common - Insomnia

Nervous system disorders

Very common - Dysgeusia, headache

Uncommon - Ageusia

Cardiac disorders

Uncommon - Congestive cardiac failure

Vascular disorders

Common - Hemorrhage^b, hypertension,

Uncommon - Deep vein thrombosis

Respiratory, thoracic and mediastinal disorders

Very common - Pneumonitis^c, epistaxis, cough,

Common - dyspnea

Uncommon - Hemoptysis, pulmonary embolism

Rare - , acute respiratory distress syndrome

Gastrointestinal disorders

Very common - Stomatitis^d, diarrhea, nausea

Common - Vomiting, dry mouth, abdominal pain, oral pain, dyspepsia, dysphagia

Skin and subcutaneous tissue disorders

Very common - Rash, pruritus

Common - Dry skin, nail disorder, acne, erythema, hand-foot syndrome

Rare - Angioedema

Musculoskeletal and connective tissue disorders

Common - Arthralgia

Renal and urinary disorders

Common - Proteinuria, Renal failure

Uncommon - Increased daytime urination, acute renal failure

Reproductive system and breast disorders

Common - Menstruation irregular^f

Uncommon - , amenorrhea

General disorders and administration site conditions

Very common - Fatigue, asthenia, edema peripheral, ,

Common - Pyrexia, mucosal inflammation

Uncommon - Non-cardiac chest pain, impaired wound healing

Investigations

Very common - Weight decreased

Common - aspartate aminotransferase increased, Alanine aminotransferase increased, blood creatinine increased

^a Includes all reactions within the 'infections and infestations' system organ class including common: pneumonia, urinary tract infection and uncommon: bronchitis, herpes zoster, sepsis, abscess and isolated cases of opportunistic infections (e.g. aspergillosis, and rare : viral myocarditis candidiasis and hepatitis B)

^b Includes different bleeding events from different sites not listed individually

^c Includes common: pneumonitis: interstitial lung disease, lung infiltration, and rare - alveolitis, pulmonary alveolar hemorrhage, and pulmonary toxicity

^d Includes very common: stomatitis; common: aphthous stomatitis, mouth and tongue ulceration; uncommon: glossitis, glossodynia

^e reported as palmar-plantar erythrodysesthesia syndrome

^f frequency is based upon number of women age 10 to 55 years of age in the study pool

IRB NUMBER: PHXB-17-0072-70-15
IRB APPROVAL DATE: 07/03/2018

Clinically relevant laboratory abnormalities

In the pooled double-blind phase III safety database, the following new or worsening clinically relevant laboratory abnormalities were reported with an incidence of $\geq 1/10$ (very common, listed in decreasing frequency).

- Hematology: hemoglobin decreased, lymphocytes decreased, white blood cells decreased, platelets decreased, and neutrophils decreased (or collectively as pancytopenia);
- Clinical chemistry: glucose (fasting) increased, cholesterol increased, triglycerides increased, AST increased, phosphate decreased, ALT increased, creatinine increased, potassium decreased, and albumin decreased.

Most of the observed abnormalities ($\geq 1/100$) were mild (grade 1) or moderate (grade 2). Grade 3/4 hematology and chemistry abnormalities include:

- Hematology: lymphocytes decreased, hemoglobin decreased, (very common); neutrophils decreased, platelet count decreased, white blood cells decreased (all common).
- Clinical chemistry: glucose (fasting) increased, phosphate decreased, potassium decreased, AST increased, ALT increased, creatinine increased cholesterol (total) increased, triglycerides increased, albumin decreased (all common).

Tuberous sclerosis complex (TSC)

The most frequent ADRs (incidence $\geq 1/10$ and suspected to be related to treatment by the investigator) from the pooled safety database are (in decreasing order): stomatitis, upper respiratory tract infections, amenorrhea, hypercholesterolemia, nasopharyngitis, acne, menstruation irregular, sinusitis, and pneumonia

The most frequent grade 3/4 adverse reactions (incidence $\geq 1/100$ to $< 1/10$ and suspected to be related to treatment by the investigator) were stomatitis, amenorrhea, pneumonia, neutropenia, pyrexia, and gastroenteritis viral.

The below table shows the incidence of ADRs based on pooled data in patients receiving everolimus in the TSC studies (including both the double-blind and open-label study and extension periods). ADRs are listed according to MedDRA system organ class. Frequency categories are defined using the following convention: very common ($\geq 1/10$); common ($\geq 1/100$ to $< 1/10$); uncommon ($\geq 1/1,000$ to $< 1/100$); rare ($\geq 1/10,000$ to $< 1/1,000$); very rare ($< 1/10,000$); not known (cannot be estimated from the available data). Within each frequency grouping, ADRs are presented in order of decreasing frequency.

Infections and infestations

Very common - Upper respiratory tract infection, nasopharyngitis, sinusitis, pneumonia

Common - Otitis media, urinary tract infection, pharyngitis, cellulitis,

pharyngitis streptococcal, gastroenteritis viral, , gingivitis

Uncommon - Herpes zoster, bronchitis viral

IRB NUMBER: PHXB-17-0072-70-15

IRB APPROVAL DATE: 07/03/2018

Blood and lymphatic system disorders

Common - Neutropenia, anemia, leukopenia, lymphopenia, thrombocytopenia

Immune system disorders

Uncommon - Hypersensitivity

Metabolism and nutrition disorders

Very common - Hypercholesterolemia

Common - Hyperlipidemia, decreased appetite, hypophosphatemia, hypertriglyceridemia

Psychiatric disorders

Common - Insomnia,

Uncommon - aggression

Nervous system disorders

Common - Headache, dysgeusia

Vascular disorders

Common - Hypertension, lymphedema

Respiratory, thoracic and mediastinal disorders

Common - Cough, epistaxis, Pneumonitis

Gastrointestinal disorders

Very common - Stomatitis^a

Common - Diarrhea, nausea, vomiting, abdominal pain, oral pain, flatulence, constipation, gastritis

Skin and subcutaneous tissue disorders

Very Common - Acne

Common - rash^b, dermatitis acneiform, dry skin

Uncommon - Angioedema

Renal and urinary disorders

Common - Proteinuria

Reproductive system and breast disorders

Very Common - Amenorrhea^c, menstruation irregular^c,

Common - menorrhagia, vaginal hemorrhage, menorrhagia, ovarian cyst, menstruation delayed^c

General disorders and administration site conditions

Common - Fatigue, pyrexia, irritability

Investigations

Common - Blood lactate dehydrogenase increased, blood luteinizing hormone increased

Uncommon - Blood follicle stimulating hormone increased

^a Includes very common: stomatitis, mouth ulceration aphthous stomatitis; uncommon: gingival pain, glossitis, lip ulceration, tongue ulceration

^b Includes common: rash, rash erythematous; uncommon: erythema, rash macular, rash maculo-papular, rash generalized.

^c frequency is based upon number of women age 10 to 55 years of age while on treatment in the safety pool

Clinically relevant laboratory abnormalities

In the pooled TSC safety database the following new or worsening clinically relevant laboratory abnormalities reported with an incidence of $\geq 1/10$ (very common, listed in decreasing frequency):

- Hematology: partial thromboplastin time increased, hemoglobin decreased, white blood cells decreased, neutrophils decreased, lymphocytes decreased, and platelet count decreased.
- Clinical chemistry: cholesterol increased, triglycerides increased, AST increased, ALT increased, phosphate decreased, alkaline phosphatase increased, potassium decreased, and glucose (fasting) increased.

Most of the laboratory abnormalities were mild (grade 1) or moderate (grade 2). Grade 3/4 hematology and chemistry abnormalities included:

- Hematology: neutrophils decreased, partial thromboplastin time increased (common) and lymphocytes decreased, hemoglobin decreased (uncommon).
- Clinical chemistry: phosphate decreased, alkaline phosphatase increased, AST increased (common); cholesterol increased, triglycerides increased, ALT increased, potassium decreased, and glucose (fasting) increased (uncommon).

Description of selected adverse drug reactions

In clinical trials and post-marketing spontaneous reports, everolimus has been associated with serious cases of the following :

- hepatitis B reactivation, including fatal outcome. Reactivation of infections is an expected event during periods of immunosuppression.
- renal failure events (including fatal ones) and proteinuria. Monitoring of renal function is recommended.
- amenorrhea (including secondary amenorrhea).
- Pneumocystis jirovecii pneumonia (PJP) some with a fatal outcome.
- Angioedema has been reported with and without concomitant use of everolimus and ACE inhibitors

The table below lists all fatal adverse events reported by investigators across all RAD001 studies as having a suspected causal relationship to everolimus and occurring on or before the cut off date of 31-Mar-2014.

MedDRA system organ class	Event
Blood and lymphatic system disorders	Thrombocytopenia
Cardiac disorders	Acute cardiopulmonary event, cardiogenic shock, cardio-respiratory arrest, myocardial infarction
Gastrointestinal disorders	Diarrhea, duodenal ulcer, GI hemorrhage, intestinal perforation, esophageal perforation, internal hernia
General disorders/administration site conditions	Cold sweat, concomitant disease progression, general physical health deterioration, multi-organ failure, sudden death
Infections and infestations	Candidal sepsis, EBV pneumonia, neutropenic sepsis, pneumocystis jirovecii pneumonia, reactivation of 0072-70-15

	Hepatitis B, septic shock, septicemia with massive Epstein-Barr viremia
Injury, poisoning and procedural complications	Bone fissure
Metabolism and nutrition disorders	Dehydration, ketoacidosis, hyperglycemia
Neoplasms benign, malignant and unspecified (including cysts and polyps)	Squamous cell carcinoma of skin
Nervous system disorders	Cerebral hemorrhage, embolic stroke, restlessness
Renal and urinary disorders	Renal tubular necrosis
Respiratory thoracic and mediastinal disorders	Acute cardiopulmonary event, acute respiratory distress syndrome, cardio-respiratory arrest, dyspnea, chronic obstructive pulmonary disease, interstitial pneumonia, pulmonary embolism, pulmonary edema, pneumonitis
Vascular Disorders	Cerebral hemorrhage, disseminated intravascular coagulation, embolic stroke, hemorrhage, hypovolemic shock, myocardial infarction, pulmonary hypertension

The table below lists all serious, unexpected, life-threatening adverse events considered related to study drug, and reported on

at least one occasion up to the cut-off date of 31-Mar-2014. It should be stressed that many of these SAE reports have been reported only on a single occasion making an accurate

assessment of causality difficult, if not impossible. Due to the imprecision of causality, the causality assessments should not be assumed that all of these events are indeed the result of therapy with everolimus. Moreover, the assessment of causality is particularly difficult in critically ill patients where confounding factors are present relating mainly to complications of the underlying disease and to the use of prior therapy and/or concomitant medications. In addition to the SAE reports presented below, disease progression has on occasions been reported somewhat paradoxically as an SAE with a suspected causal relationship to everolimus and reported on at least one occasion.

Individual events are presented for each MedDRA system organ class.

MedDRA system organ class	Event
Blood and lymphatic system disorders	Acute leukemia, anemia, bone marrow failure, disseminated intravascular coagulation, febrile neutropenia , hemorrhagic diathesis, leukemoid reaction, leukocytosis, leukopenia, lymphadenopathy, lymphedema, lymphopenia, neutropenia, pancytopenia, platelet disorder, retroperitoneal lymphadenopathy, thrombocytopenia, white blood cell disorder, hemolytic uremic syndrome
Cardiac disorders	atrial fibrillation, atrioventricular block, ardiorespiratory arrest , cardiopulmonary arrest, congestive cardiomyopathy, cyanosis, diastolic dysfunction, dilatation left atrial and left ventricular, hypertrophy, left ventricular hypertrophy, left ventricular dysfunction , myocardial infarction, myocardial ischemia, hypertensive heart disease, palpitations, pericardial effusion, right ventricular failure, sinus tachycardia, stress cardiopathy, supraventricular tachycardia, tachycardia, ventricular dysfunction Valve incompetence: mitral/pulmonary/tricuspid
Ear and labyrinth disorders	Vertigo, sudden hearing loss, deafness unilateral
Endocrine disorders	Hyperthyroidism, hyperglycemic non-ketotic syndrome, hypercalcemia, hypothyroidism

Eye disorders	Conjunctivitis, eyelid edema, scleral discoloration, ocular discomfort, ocular surface disease, phthalmoplegia_crani nerve paralysis, papilloedema, photophobia, retinal artery thrombosis, retinal detachment, retinal hemorrhage, steroid Induced cataract, senile cataract, visual acuity reduced.
